9.1.2.3.1. American College of Rheumatology Core Set

a. Tender Joint Count

TJC joint assessments will be performed by a blinded assessor.

For ACR measures, the number of tender and painful joints will be determined by examination of 68 joints (34 joints on each side of the patient's body). Any joints that require intra-articular injections during the study (according to Section 7.7) should be excluded from evaluation from the time of the injection to the conclusion of the study.

Joints will be assessed for tenderness by pressure and joint manipulation on physical examination. The patient will be asked for pain sensations on these manipulations and watched for spontaneous pain reactions. Any positive response on pressure, movement, or both will then be translated into a single tender-versus-nontender dichotomy.

Missing, replaced, ankylosed, or arthrodesed joints will be identified by the investigator at the Screening Visit and will be excluded from evaluation during the trial.

b. Swollen Joint Count

SJC joint assessments will be performed by a blinded assessor.

For ACR measures, the number of swollen joints will be determined by examination of 66 joints (33 joints on each side of the patient's body). Any joints that require intra-articular injections during the study (according to Section 7.7) should be excluded from evaluation from the time of the injection to the conclusion of the study.

Joints will be classified as either swollen or not swollen. Swelling is defined as palpable fluctuating synovitis of the joint. Swelling secondary to osteoarthritis will be assessed as not swollen, unless there is unmistakable fluctuation. Dactylitis should be counted as 1 swollen joint.

Missing, replaced, ankylosed, or arthrodesed joints will be identified by the investigator at the Screening Visit and will be excluded from evaluation during the trial.

c. Patient's Assessment of Pain Visual Analog Scale

The patient will be asked to assess his or her current level of joint pain by marking a vertical tick on a 100-mm horizontal VAS where the left end represents no joint pain and the right end represents worst possible joint pain. The Patient's Assessment of Pain VAS should be administered *prior to* the TJC and SJC examinations.

Results will be expressed in millimeters measured between the left end of the scale and the crossing point of the vertical line of the tick; this procedure is applicable for all VAS used in the trial.

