9.1.2.7. Minimal Disease Activity

The MDA score has been developed based on current expert opinion and uses a composite of 7 key outcome measures used in PsA to encompass all of the domains of the disease to measure

the overall state of a patient's disease (Coates et al. 2010a; Coates and Helliwell 2010b). The overall state of disease activity is deemed a useful target of treatment by both the patient and the physician, given current treatment possibilities and limitations. Preliminary validation work supports the use of the MDA criteria in both observational cohorts and in interventional trial cohorts. The PsA MDA criteria have evidence supporting their use within the OMERACT filter of truth, discrimination, and feasibility.

• MDA: Patients are classified as achieving MDA if they fulfill 5 of 7 outcome measures: TJC ≤1; SJC ≤1; psoriasis activity and severity index (PASI total score) ≤1 or BSA ≤3; patient pain VAS score of ≤15; patient global disease activity VAS score of ≤20; HAQ-DI score ≤0.5; and tender entheseal points ≤1.

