Nail Psoriasis Severity Index (NAPSI)	NAPSI will be used if the patient has fingernail psoriasis at baseline. The NAPSI is a numeric, reproducible, objective tool for evaluation of fingernail psoriasis. This scale is used to evaluate the severity of fingernail bed psoriasis and fingernail matrix psoriasis by area of involvement in the fingernail unit. In this study, only fingernail involvement will be assessed. The fingernail is divided with imaginary horizontal and longitudinal lines into quadrants. Each fingernail is given a score for fingernail bed psoriasis (0-4) and fingernail matrix psoriasis (0-4), depending on the presence (score of 1) or absence (score of 0) of any of the features of fingernail bed and fingernail matrix psoriasis in each quadrant: 0 = None 1 = present in one quadrant of nail 2 = present in two quadrants of nail 3 = present in three quadrants of nail 4 = present in four quadrants of nail	
 NAPSI score 	The NAPSI score of a fingernail is the sum of scores in fingernail bed and fingernail matrix from each quadrant (maximum of 8). Each fingernail is evaluated, and the sum of all the fingernails is the total NAPSI score (range, 0 to 80), usually indicated as NAPSI score.	For each fingernail, if either the bed or matrix score is missing or not done, then the score for that finger is missing. If <50% of the finger scores from 10 fingers are missing, the imputation will be performed by using the average score of the remaining fingernails. If ≥50% of the finger scores are missing, the NAPSI score will be left as missing
		
 Change from baseline in NAPSI score 	Calculated as: observed NAPSI – baseline NAPSI	Missing if baseline or observed value is missing
		
 NAPSI = 0 	NAPSI score equals to 0, indicating resolution of nail psoriasis.	Single item, missing if observed NAPSI score missing.
Tender Joint Count (TJC) (68 joint count)	The number of tender and painful joints will be determined by examination of 68 joints (34 joints on each side of the patient’s body). The 68 joints to be assessed and classified	
 TJC score 	Adjusted sum of the painful/tender joints for all 68 joints: (sum of the evaluable individual joint	If more than half of the joint scores are nonevaluable, the total score will be missing.

Measure	Description	Variable	Derivation/Comment	Imputation Approach if with Missing Components

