	as tender or not tender.		
$scores)/(number\ of\ evaluable\ joints) \times 68$
 
See Appendix 3 for complete details.
	
		
 Change from baseline in TJC score 	Calculated as: observed TJC score – baseline TJC score	Missing if baseline or observed value is missing
Swollen Joint Count (SJC) (66 joint count)	The number of swollen joints will be determined by examination of 66 joints (33 joints on each side of the patient’s body). The 66 joints to be assessed and classified as swollen or not swollen.	
 SJC score 	
Adjusted sum of the swollen joints for all 66 joints: $(sum\ of\ the\ evaluable\ individual\ joint\ scores)/(number\ of\ evaluable\ joints) \times 66$
 
See Appendix 3 for complete details.
	If more than half of the joint scores are nonevaluable, the total score will be missing.
		
 Change from baseline in SJC score 	Calculated as: observed SJC score – baseline SJC score	Missing if baseline or observed value is missing
Patient’s Assessment of Pain Visual Analog Scale (VAS)	Assesses the patient’s current level of joint pain by marking a vertical tick on a 100-mm horizontal VAS.	
 Patient’s pain VAS score 	Range: 0 to 100 mm 0 represents no joint pain 100 represents the worst joint pain	Single item, missing if missing
		
 Change from baseline in patient’s pain VAS score 	Calculated as: observed patient’s pain VAS– baseline patient’s pain VAS	Missing if baseline or observed value is missing
Patient’s Global Assessment of Disease Activity Visual Analog Scale (VAS)	Assesses the patient’s overall assessment of his or her PsA activity by marking a 100-mm horizontal VAS.	
 Patient’s global assessment VAS score 	Range: 0 to 100 mm 0 represents no disease activity 100 represents extremely active disease activity	Single item, missing if missing

Measure	Description	Variable	Derivation/Comment	Imputation Approach if with Missing Components
		
 Change from baseline in patient’s global assessment VAS score 	Calculated as: observed patient’s global assessment VAS– baseline patient’s global assessment VAS	Missing if baseline or observed value is missing

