	
a patients' disease (Coates et al. 2010a; Coates and Helliwell 2010b). The LEI is used to assess tender enthesal points.
		
measures: TJC ≤ 1 SJC ≤ 1 PASI total score ≤ 1 or BSA ≤ 3 patient pain VAS score of ≤ 15 patient global assessment VAS score of ≤ 20 HAQ-DI score ≤ 0.5 tender enthesal points (6 enthesal points) ≤ 1
	
the result is missing.

Coates criteria for Minimal Disease Activity (MDA) (18 enthesal points)
	
Uses a composite of 7 key outcome measures (includes PASI) used in PsA to encompass all of the domains of the disease to measure the overall state of a patients' disease (Coates et al. 2010a; Coates and Helliwell 2010b). The LEI and SPARCC are used to assess tender enthesal points.
	
Proportion of patients achieving Coates criteria for MDA (18 enthesal points)
	
Patients are classified as achieving Coates criteria for MDA (18 enthesal points) if they fulfill 5 of 7 outcome measures: TJC ≤ 1 SJC ≤ 1 PASI total score ≤ 1 or BSA ≤ 3 patient pain VAS score of ≤ 15 patient global VAS score of ≤ 20 HAQ-DI score ≤ 0.5 tender enthesal points ≤ 1 (based on 18 enthesal points)
	
If the patient achieves MDA with the non-missing measures, then impute as achieving MDA; otherwise, the result is missing.

Leeds Enthesitis Index (LEI)
	
For patients with enthesitis, an assessment that consists of 18 enthesal points is performed by site personnel. The LEI has been developed specifically for use in PsA and measures enthesitis at 6 sites (lateral epicondyle [left and right],
	
LEI score
	
Each of the 6 sites is assigned a score of 0 (absent) or 1 (present) and the results are added to produce a total score (range: 0-6).
	
If one or more of the 6 sites are missing, then set LEI score to missing.

		
Change from baseline in LEI
	
Calculated as: observed LEI score – baseline LEI score
	
Missing if baseline or observed value is missing

Measure	Description	Variable	Derivation/Comment	Imputation Approach if with Missing Components
	medial femoral condyle [left and right], and Achilles tendon insertion [left and right]) (Healy and Helliwell 2008).	
 LEI score = 0 	LEI score equals to 0, indicating complete resolution in enthesitis.	Missing if observed value are missing

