Appendix 3. Algorithm for Calculating Joint Counts

Joints are evaluated and recorded as either non-evaluable, or if evaluable, then if tenderness is present or absent, and if swelling is present or absent. In total, 68 joints are assessed for tenderness and 66 are assessed for swelling. Hips are not assessed for swelling.

The number of tender/swollen joints will be calculated by summing all joints checked to have tenderness/swelling present. If at least half but not all of the joints are evaluable, then the observed prorated joint count will be calculated instead. The prorated scores for TJC will be adjusted based upon the number of evaluable joints: the counted score will be multiplied by 68 then divided by the number of joints evaluated (excluding non-evaluable joints and any joints with a missing response). For example: if only 60 of the 68 joints are assessed to be evaluable at a visit, and 32 of those 60 are tender, the prorated joint count is $(32/60) \times 68 = 36.27$ (not 32). The prorated joint count will be rounded up to the next integer and be used in calculating the percent change from baseline in TJC. The same algorithm will be applied to the calculation of percent change from baseline in SJC with the exception that the counted score will be multiplied by 66 then divided by the number of joints evaluated. If less than half of the joints are evaluable, the number of tender/swollen joints is missing.

This same algorithm will be used for the calculation of TJC and SJC based on 28 joints, which is part of the 28 diarthrodial joint count, based on C-reactive protein (DAS28-CRP) score.

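### Read literally, the SAP applies the MDA limits TJC ≤1 and SJC ≤1 to prorated joint counts, so one active joint plus a non-evaluable joint fails the criterion

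*SAP*

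**What the plan says.** **Joint counts.** SAP Section 6.12, Table RHCF.6.3, gives one definition for each score. TJC is the "Adjusted sum of the painful/tender joints for all 68 joints": tender joints divided by evaluable joints, times 68. SJC is the "Adjusted sum of the swollen joints for all 66 joints", built the same way with 66. The table defines no separate raw-count variable.

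**Proration.** SAP Appendix 3 starts from a simple sum of active joints and then says: "If at least half but not all of the joints are evaluable, then the observed prorated joint count will be calculated instead". On rounding: "The prorated joint count will be rounded up to the next integer and be used in calculating the percent change from baseline in TJC". At the lower end: "If less than half of the joints are evaluable, the number of tender/swollen joints is missing". Hips are assessed for tenderness but not for swelling.

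**MDA.** The SAP has two MDA rows, for 6 and 18 entheseal points. The second reads: "Patients are classified as achieving Coates criteria for MDA (18 enthesal points) if they fulfill 5 of 7 outcome measures". Two of the seven measures in each row are TJC ≤1 and SJC ≤1. Neither row says which form of the count is meant. Protocol Section 9.1.2.7 sets the same limits ("Patients are classified as achieving MDA if they fulfill 5 of 7 outcome measures") and does not mention scaling.

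**Non-evaluable joints.** Under Protocol Section 9.1.2.3.1, missing, replaced, ankylosed or arthrodesed joints "will be excluded from evaluation during the trial". A joint injected during the study is excluded from the injection to the end of the study. Appendix 3 also leaves joints with a missing response out of the denominator.

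**The concern.** Proration is reasonable for a count that is analysed as a change or percent change, because numerator and baseline are put on the same scale. An absolute cut-off of one joint is different. Any upward scaling of a count of 1, however slight, takes it past the limit, so the criterion stops meaning at most one active joint and comes to mean none.

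This would apply only to patients with non-evaluable joints, some of whom have replaced or fused joints. A patient with one residual tender or swollen joint would lose a criterion for a reason unrelated to current disease activity. A patient with one of each would lose two. Some would then fall below 5 of 7 and count as MDA non-responders. MDA is a listed secondary endpoint, compared between arms at each post-baseline visit (SAP Table RHCF.6.4). Two programmers could also code the rule differently, because the SAP never says which count the MDA rows take.

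**Working it through.** **Inputs.** The formulas come from Table RHCF.6.3 and Appendix 3: TJC = tender / evaluable × 68 and SJC = swollen / evaluable × 66, used when at least half but not all joints are evaluable. The MDA limits are TJC ≤1 and SJC ≤1.

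**Reproducing the SAP's example.** Appendix 3 takes 32 tender joints among 60 evaluable: 32/60 × 68 = 36.27, as stated there; rounded up, 37.

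**Same formula with one active joint.**

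| Non-evaluable joints | TJC, unrounded | SJC, unrounded | If rounded up | Limit ≤1 met? |
|---|---|---|---|---|
| 0 | 68/68 = 1.000 | 66/66 = 1.000 | 1 | Yes |
| 1 | 68/67 = 1.015 | 66/65 = 1.015 | 2 | No |
| 8 | 68/60 = 1.133 | 66/58 = 1.138 | 2 | No |
| Half (34 of 68; 33 of 66) | 68/34 = 2.000 | 66/33 = 2.000 | 2 | No |

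For every number of non-evaluable joints from 1 to half, the score is above 1 before any rounding. Removing the round-up would therefore not cure the problem. With zero active joints the score is 0 and the limit is met; with two or more it fails under either count. Only a count of exactly one is affected.

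**Where the result does not apply.**
- A non-evaluable hip enters the TJC denominator but not the SJC denominator.
- With fewer than half of the joints evaluable, the count is missing rather than above 1. MDA is then credited if the non-missing measures already reach 5; otherwise it is missing, and non-responder imputation treats it as failure (SAP Section 6.4.1).

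**When MDA status changes.** A patient who loses one joint criterion changes status only if exactly five criteria were met with the observed count. A patient who loses both changes status if five or six were met.

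**Size.** The effect on the MDA rate is roughly the share of patients with a non-evaluable joint, times the share with exactly one active joint, times the share of those at the boundary. The documents give none of the three. With purely assumed, independent inputs of 5% to 15%, 16% to 24% and 20% to 30%, the product runs from 0.05 × 0.16 × 0.20 = 0.16% to 0.15 × 0.24 × 0.30 = 1.08%. In an arm of 275 that is about 0.4 to 3 patients. This shows only what order of effect such inputs would give; it is not an estimate for this trial.

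**The case against.** The strongest reply is that the SAP never states that MDA uses the prorated score. The MDA rows name TJC and SJC only. Appendix 3 begins with a plain sum, and the uses it names for the prorated count are percent change from baseline and the 28-joint counts in DAS28-CRP. A programmer might take the observed count for MDA without breaking any explicit sentence. This is fair, and it is why the point is put as a literal reading. It does not remove the point: the only TJC and SJC variables defined in the table are prorated, Appendix 3 substitutes the prorated count for the sum, and no exception is written.

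A second reply is that proration is the cautious choice. An observed count treats every non-evaluable joint as inactive. With 34 of 68 joints evaluable and one tender, the observed rate corresponds to 2 of 68, yet the observed count would pass. This stands as a real cost when many joints are non-evaluable. It carries little weight for one or a few, where a score of 1.015 hardly suggests a second active joint.

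A reader might infer more than the documents support:
- *That the SAP contradicts the protocol.* Protocol Section 9.1.2.7 gives the limits but no derivation, and Section 10.3.1 leaves complete analysis details to the SAP. There is no direct contradiction.
- *That the modified CPDAI shifts in the same way.* Four tender joints with one non-evaluable joint score 4 × 68/67 = 4.06, above that index's limit of 4. But the categories in SAP Appendix 5 are worded as TJC or SJC, and they overlap. Whether the patient changes category depends on how that wording is resolved, so a shift is not established.
- *That rounding to the nearest integer would cure it.* It stops returning 1 at 23 non-evaluable joints for TJC (68/45 = 1.51) and at 22 for SJC (66/44 = 1.50), both within the range where the SAP prorates.

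**Conclusion.** The concern holds as a literal reading of the SAP. For a patient with exactly one tender joint and at least one of the 68 joints non-evaluable, or exactly one swollen joint and at least one of the 66 non-evaluable, the limit of one joint becomes a limit of zero, provided at least half of the joints are evaluable. That arithmetic needs no assumption beyond the MDA rows taking TJC and SJC as the table defines them.

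The consequence for the trial is probably small, and it cannot be sized from the documents. Only patients at the 5-of-7 boundary change status. MDA is outside the multiplicity procedure (SAP Sections 6.6 and 6.12.1.3). ACR50 and PASI 100, which make up the primary and major secondary endpoints, rest on percent improvement and do not use these cut-offs.

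A reader might also infer a bias between the arms. The documents do not show one: the rule is the same in both arms, and it tends to lower the MDA rate in each. Equal effect is not guaranteed at later visits, because joints injected after randomization also become non-evaluable and treatment is open-label, but nothing in the documents indicates a difference or its direction.

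**What to change.** Add one sentence to the MDA rows of Table RHCF.6.3 or to Appendix 3: the MDA limits TJC ≤1 and SJC ≤1 use the observed, unprorated count when at least half of the joints are evaluable, and the count is missing otherwise. Keep prorated counts for change and percent change from baseline and for DAS28-CRP.

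The cost is that sentence and a small change to the derivation program, with no new data. The SAP should acknowledge the trade-off: the observed count treats non-evaluable joints as inactive, which is lenient when many are non-evaluable. If the sponsor does intend the prorated count for MDA, the SAP should say so explicitly, so that the stricter criterion for these patients is a stated choice.

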10.3.1.2.1. Nonresponder Imputation

Missing data for categorical efficacy and health outcome measures will be imputed using the nonresponder imputation (NRI) method. Patients will be considered nonresponders if they do not meet the clinical response criteria or have missing clinical response data at the time point of analysis. Randomized patients without at least one post-baseline observation will also be defined as nonresponders for the NRI analysis.

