6.4. Handling of Dropouts or Missing Data

6.4.1. Non-Responder Imputation (NRI) for Clinical Response

Analysis of categorical efficacy and health outcome variables will be based on treatment success/failure. This approach yields results numerically identical to non-responder imputation (NRI), but it is interpreted differently. Patients will be considered treatment failures (or non-responders) if they do not meet the clinical response criteria or have missing clinical response data at a particular time point of analysis.

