		
 Change from baseline in CRP (mg/L) 	Calculated as: observed CRP – baseline CRP	Missing if baseline or observed value is missing
Psoriatic Arthritic Response Criteria (PsARC)	
PsARC is a composite criteria reported in terms of the percentage of patients achieving response according to the following criteria: PGA, PatGA, TJC, and SJC. Overall response is defined by improvement from the baseline assessment in 2 of the 4 criteria, 1 of which must be a joint count; there must not be worsening in any of the 4 criteria:
 
At least 30% reduction in TJC At least 30% reduction in SJC At least a 1-point reduction in physician’s assessment At least a 1-point reduction in patient’s assessment
 
The PsARC response was modified in this study by using the PGA and the PatGA on a 100-mm VAS instead of a 5-point Likert scale in the original criteria. The results from the 2 VAS measures were assessed as a difference from baseline (in mm), and criteria 3 and 4, above, were changed to “at least a 20 mm reduction” (Clegg 1996).
	PsARC	
Overall response is defined by improvement from the baseline assessment in 2 of the 4 criteria, 1 of which must be a joint count; there must not be worsening in any of the 4 criteria:
 
At least 30% reduction in TJC At least 30% reduction in SJC At least a 20-mm reduction in physician’s assessment At least a 20-mm reduction in patient’s assessment
	If the patient achieves PsARC with the non-missing measures, then impute as achieving PsARC; otherwise, the result is missing.
Coates criteria for Minimal Disease Activity (MDA) (6 enthesal points)	Uses a composite of 7 key outcome measures (includes PASI) used in PsA to encompass all of the domains of the disease to measure the overall state of	Coates criteria for MDA (6 enthesal points)	Patients are classified as achieving Coates criteria for MDA (6 enthesal points) if they fulfill 5 of 7 outcome	If the patient achieves MDA with the non-missing measures, then impute as achieving MDA; otherwise,

Measure	Description	Variable	Derivation/Comment	Imputation Approach if with Missing Components

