		
 • Change from baseline in DAS28-CRP 	Calculated as: observed DAS28-CRP score – baseline DAS28-CRP score	Missing if baseline or observed value are missing
Modified Composite Psoriatic Disease Activity Index (mCPDAI)	
A validated instrument to assess composite psoriatic disease activity and response to therapy (Mumtaz et al. 2011). This instrument assesses individual domains:
 
 • peripheral arthritis as assessed by the number of tender and swollen joints and the HAQ-DI • skin as assessed by the PASI and the Dermatology Life Quality Index (DLQI) 	
 • mCPDAI total score 	Each domain with the exception of spinal disease is scored from 0-3. Individual domain scores are summed to give an overall composite score (range 0-12) with a higher score indicating higher disease activity (see Appendix 5).	If 1 or more components are missing, then set to missing.

Measure	Description	Variable	Derivation/Comment	Imputation Approach if with Missing Components
		
 Change from baseline in mCPDAI total score 	Calculated as: observed mCPDAI score – baseline mCPDAI score	Missing if baseline or observed value are missing
		
 mCPDAI ≤ 5 	mCPDAI score ≤ 5 , indicating low disease activity or remission in modified CPDAI (Salaffi et al. 2014)	Missing if observed mCPDAI is missing

Abbreviations: BSA = body surface area; eCRF = electronic case report form; PsA = psoriatic arthritis.

Table RHCF.6.4. Description of Primary and Secondary Efficacy Analyses

Measure	Variable	Analysis Method (Section 6.2)	Population (Section 6.1.3)	Comparison/Time Point	Analysis Type
Composite endpoint of American College of Rheumatology (ACR) 50 and Psoriasis Area and Severity Index (PASI) 100	
 Proportion of patients with ACR50 and PASI 100 simultaneously (Primary Endpoint at Week 24) 	Logistic regression using the NRI method (see Section 6.4.1)	ITT population	IXE vs ADA at Week 24 and all other post-baseline visits	Primary analysis (IXE vs ADA at Week 24) Secondary analysis
		Fisher’s exact test using the NRI method (see Section 6.4.1)	ITT population	IXE vs ADA at Week 24 and all other post-baseline visits	Secondary analysis

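### PsARC is imputed as achieved from the non-missing items, but its no-worsening condition covers all four items and cannot be checked when one is missing; the effect is small

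*SAP*

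**What the plan says.** SAP Table RHCF.6.3 (Section 6.12) defines a PsARC response by two conditions. The first is "improvement from the baseline assessment in 2 of the 4 criteria, 1 of which must be a joint count". The second is that "there must not be worsening in any of the 4 criteria". The four items are the tender joint count, the swollen joint count, the physician's global and the patient's global. The row gives thresholds for improvement (30% for the joint counts, 20 mm for the globals) but none for worsening.

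The missing-component cell of that row reads: "If the patient achieves PsARC with the non-missing measures, then impute as achieving PsARC". In every other incomplete case it sets the result to missing. A result left missing is then handled by SAP 6.4.1, which treats patients as failures if they do not meet the criteria or "have missing clinical response data at a particular time point of analysis". Protocol 10.3.1.2.1 says the same: "have missing clinical response data at the time point of analysis".

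PsARC is an other secondary endpoint. Table RHCF.6.4 compares it between arms at every post-baseline visit by logistic regression with nonresponder imputation (NRI). SAP 6.6 leaves it outside the alpha-controlled sequence.

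**The concern.** The second condition is a veto: worsening in a single item cancels the response, however good the other three are. A patient with one item missing may have worsened on exactly that item. The cell nevertheless calls the patient a responder, and does so before NRI can act. The definition and the missing-data rule in the same row therefore do not fit together.

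At stake is the PsARC response rate at each visit, and possibly the comparison between arms if incomplete visits were more common in one arm. There is also a reproducibility problem, because the SAP does not say how the no-worsening condition is to be judged for an item that was not recorded.

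**Working it through.** The documents state no PsARC rate, worsening rate or item-missingness rate, so there is no figure of the plan's own to reproduce. The logic can be checked exactly. The size can only be illustrated.

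**1. Comparison with the plan's other composites**

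- MDA (Table RHCF.6.3) has the same wording: "If the patient achieves MDA with the non-missing measures, then impute as achieving MDA; otherwise, the result is missing". It is safe there. MDA is a count of 5 out of 7 with no veto, so a missing item cannot undo a count already reached.
- ACR response (SAP Appendix 2): if one joint count is missing and the other meets the threshold, the response is left blank, because a mandatory condition is unverified. Up to two of the five remaining items may be missing, but a response still needs three observed items at the threshold, and a missing item cannot reverse that.
- mCPDAI (Table RHCF.6.3): "If 1 or more components are missing, then set to missing".

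PsARC is the composite where a missing item can overturn a response that the cell has already credited.

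**2. Enumeration**

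Code each item as worsened, unchanged or improved, and remove one item. The three observed items have 3 × 3 × 3 = 27 patterns.

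| Missing item | Patterns that achieve PsARC on the other three | Of these, response certain on all four | Patterns not achieving on three that could be responses on four |
|---|---|---|---|
| A joint count | 3 | 0 | 4 |
| A global | 4 | 0 | 2 |

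Example with the tender joint count missing: the swollen count must have improved, at least one global must have improved, and nothing observed may have worsened. That gives three patterns. In each of them a worsened tender count would make the patient a nonresponder.

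The last column matters as well. Those patients become missing under the cell and then nonresponders under NRI, although some of them would be true responders.

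**3. Size against strict NRI (any missing item counts as nonresponse)**

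Assumptions: a share q = 0.5% to 5% of patients has exactly one item missing at a visit, and a share R = 40% to 60% of these qualifies on the other three. Each arm has 275 patients (SAP 5.2).

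Extra responders per arm = q × R:

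- low: 0.005 × 0.4 = 0.002, or 0.2 points; × 275 = 0.55 patients
- high: 0.05 × 0.6 = 0.03, or 3.0 points; × 275 = 8.25 patients

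**4. How many credited responders are false, and the net direction**

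An illustrative simulation used four correlated items with one missing at random. It covered correlations of 0.3, 0.5 and 0.7, a probability of improvement per item of 0.50 or 0.65, and a probability of worsening per item of 0.02, 0.05, 0.10 or 0.20: 3 × 2 × 4 = 24 scenarios. Results among patients with one item missing, averaged over which item it is:

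- credited responders who are nonresponders on all four items: 0.0 to 5.7 points, or 0% to about 12% of those credited
- true responders counted as nonresponders: 3.7 to 13.3 points
- net against the true four-item rate: −13.0 to +1.7 points, negative in 22 of 24 scenarios

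The two positive scenarios have 20% worsening and 65% improvement per item. With a global as the missing item, the net reaches at most +4.5 points.

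False responders per arm at the upper end: 8.25 × 0.12 ≈ 1.0 patient.

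**The case against.** **The cell is two-sided.** It ends by setting every other incomplete case to missing, and NRI turns those into nonresponses. A reader might infer that the PsARC rate is overstated. The documents do not support that: it is certain only relative to strict NRI. Against the true four-item rate the direction is open, and in most scenarios tried it was downward. This part of the objection stands.

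**Strict NRI is not more accurate.** If 88% to 100% of the credited patients are true responders, the replacement turns them all into nonresponders: 0.88 × 0.2 ≈ 0.2 points up to 1.00 × 3.0 = 3.0 points. This also stands. The case for the change is that it follows the endpoint's definition and the plan's treatment-failure principle, not that it comes closer to the truth.

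**There is no literal conflict with SAP 6.4.1.** Table RHCF.6.3 decides when a composite is missing, and 6.4.1 acts afterwards. That is fair: the departure is from a conservative principle, not a breach of that section's wording. But the tolerance of missing data elsewhere does not rescue the cell. ACR tolerates only items that cannot undo a success, and the joint-count proration (Appendix 3) and the HAQ-DI 6-of-8 rule (Appendix 4) are scoring rules within a single scale.

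**Perhaps PsARC can be achieved only when all four items are known.** On that reading the cell never imputes anyone and has no purpose, so it would still need rewriting.

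**Bias in the comparison.** The two globals are not on the blinded-assessor list in Protocol 7.3, and allocation is open. A reader might infer that these items go missing more often, or unequally by arm, and so favor one drug. Nothing in the documents shows this. All four items are scheduled at the same visits, and missing ACR data, which include all four, are tracked as important protocol violations (SAP Table RHCF.6.9).

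**Conclusion.** Wrong as written, with a small effect. The logical fault needs no assumed rate: with one item missing, no observed pattern guarantees a PsARC response, yet the cell credits one. Relative to strict NRI the rule can only add responders, by about 0.2 to 3 points per arm, with at most about 1 false responder per arm. Those sizes rest wholly on the assumed missingness, qualifying share, improvement and worsening rates, and on one item being missing at random. Neither the net direction against the true rate nor any effect on the difference between arms is determined by the documents. PsARC lies outside the testing sequence, so no primary or major secondary conclusion changes.

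**What to change.** Replace the missing-component cell for PsARC in Table RHCF.6.3 with: If any of the four components is missing, PsARC is missing (nonresponder under NRI), unless the non-missing items already show nonresponse. The last clause only separates observed from imputed nonresponse and does not change the NRI result.

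Report by arm and visit the number of patients affected. If wanted, keep the current rule as a sensitivity analysis, stating that no-worsening is then judged on the observed items only. While the row is open, it should also state what counts as worsening for each item.

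The cost is one SAP cell and a short count table, with no new data. The downside is that some true responders with one missing item are counted as nonresponders, so PsARC rates may fall slightly.
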